9.2.4 Patient Populations for Analysis

Five analysis populations will be defined for use with various analyses. The following table illustrates the relationship between each population and the analyses for which the data from the population will be used.

Table 8: Patient Population for Analysis

| | Analysis | | | | |
|-----------------------|----------|---------------------|-------------------------------|--------|-------------|
| Analysis Population | Baseline | Patient Disposition | Effectiveness/ Performance | Safety | Product Use |
| Screened | | x | | | |
| Intent-to-treat (ITT) | х | x | | | |
| Safety | | | | Х | х |
| Effectiveness | | | Х | | |
| Per-protocol | | | Χ [†] | | |

[†] Analysis done only if any data from more than 5% of effectiveness analysis population patients are excluded from this population.

9.2.5 Screened

The screened analysis population will include patients who signed the informed consent and were assessed for meeting the inclusion/exclusion criteria. The screened analysis set will be used in reporting the study disposition of study participants.

9.2.6 Intent-to-treat (ITT) Analysis Population

The Intent-To-Treat (ITT) analysis population in this prospective randomized study may include a small subset of patients in the screened analysis population who meet the inclusion/exclusion criteria and are randomized to either early or late vascular access but received cannulation outside their specified time period. The ITT analysis population will be used in reporting outcomes based on their randomized access time and not on the access time they received. In other words, all participants who are randomized are analyzed according to the group they were originally assigned, regardless of what access time (if any) they received.

9.2.7 Safety

The safety analysis population will include a subset of patients in the screened analysis population who are implanted with the Artegraft, regardless of whether randomized early or late vascular access is performed. The safety analysis population will be used in reporting safety and product use characteristics.

9.2.8 Effectiveness

The effectiveness analysis population will include a subset of the ITT analysis population who are implanted with the Artegraft based on the randomized early or late vascular access with the applicable

Artegraft, Inc. Version 4.0 21June2019
Protocol: ARTCT.BEACH.001 CONFIDENTIAL Page 45 of 81

performance/effectiveness responses reported for each randomized group. The effectiveness analysis population will be used in reporting the performance /effectiveness of the randomized early or late vascular access groups.

9.2.9 Per-protocol

The per-protocol analysis population will include a subset of patients in the effectiveness analysis population with no pre-specified major protocol violations or deviations. The per-protocol analysis population will be used in reporting the performance /effectiveness of the randomized groups, if the number of patients in this analysis population differs from the number of patients in the effectiveness analysis population by more than 5 percent.

9.3 Patient Discontinuation/Withdrawal from the Study

- A patient may withdraw from the study at any time at his/her own request or may be withdrawn at any time at the discretion of the Investigator for safety, behavioral, compliance, or administrative reasons.
- If the patient withdraws consent for disclosure of future information, the Sponsor may retain and continue to use any data collected before such a withdrawal of consent.
- If a patient withdraws from the study, he/she may request destruction of any samples taken and not tested, and the Investigator must document this in the study center study records.
- See SoA (Table 1) for data to be collected at the time of study discontinuation and follow-up and for any further evaluations that need to be completed.

9.4 Lost to Follow-up

A patient will be considered lost to follow-up if he or she repeatedly fails to return for scheduled visits and is unable to be contacted by the study center.

The following actions must be taken if a patient fails to return to the clinic for a required study visit:

- The study center must attempt to contact the patient and reschedule the missed visit as soon as possible and counsel the patient on the importance of maintaining the assigned visit schedule and ascertain whether the patient wishes to and/or should continue in the study.
- Before a patient is deemed lost to follow-up, the Investigator or designee must make every effort
 to regain contact with the patient (where possible, 3 telephone calls and, if necessary, a certified
 letter to the subject's last known mailing address or local equivalent methods). These contact
 attempts should be documented in the subject's medical record.
- Should the patient continue to be unreachable, he/she will be considered to have withdrawn from the study.

Artegraft, Inc. Version 4.0 21June2019
Protocol: ARTCT.BEACH.001 CONFIDENTIAL Page 46 of 81

10.0 SAFETY ASSESSMENTS AND PROCEDURES

- Study procedures and their timing are summarized in the SoA (Table 1).
- Protocol waivers or exemptions are not allowed.
- Adherence to the study design requirements, including those specified in the SoA (Table 1), is essential and required for study conduct.
- All screening evaluations must be completed and reviewed to confirm that potential patients meet all eligibility criteria. The Investigator will maintain a screening log to record details of all patients screened and to confirm eligibility or record reasons for screening failure, as applicable.
- Procedures conducted as part of the subject's routine clinical management (e.g., blood count) and
 obtained before signing of the ICF may be used for screening or baseline purposes provided the
 procedures met the protocol-specified criteria and were performed within the period defined in the
 SoA (Table 1).

10.1 Safety Assessments

10.2 Adverse Events

The definitions of SAE can be found in Appendix 4.

Adverse events will be reported by the patient (or, when appropriate, by a caregiver, surrogate, or the participant's legally authorized representative) or may be obtained from the patient's dialysis center.

The Investigator and any designees are responsible for detecting, documenting, and recording events that meet the definition of an AE or SAE and remain responsible for following up AEs that are serious, considered related to the study device or study procedures, or that caused the subject to discontinue the Artegraft device(see Section 8.0 Study Procedures).

Expected Adverse Events

Table 9: Expected Procedure-Related Adverse Events

| Bleeding |
|--|
| Death |
| Disruption or tearing of the suture line, graft, or host vessel |
| Embolism |
| Graft redundancy |
| Intervention complication (e.g., venous rupture) |
| Occlusion |
| Pain |
| Thrombosis |
| Technical complications (anastomosed to diseased vessel; graft physically compressed; incorrect sizing; implant technique; radiology infiltrated graft; bleeding from native vessel) |

Artegraft, Inc. Version 4.0 21June2019
Protocol: ARTCT.BEACH.001 CONFIDENTIAL Page 47 of 81

Table 10: Expected Device-Related Adverse Events

| Access failure; loss of access |
|--|
| Aneurysm |
| Bleeding |
| Cannulation-associated complication / trauma |
| Death |
| Embolic event |
| Graft dilatation |
| Hand ischemia, acute |
| Hand ischemia, subacute (delayed but w/in 1 month of implant) |
| Hematoma |
| Hemorrhage |
| Infection (cellulitis, abscess, septic emboli, bacteremia, sepsis) |
| Intervention (surgical, angioplasty, stenting, thrombectomy, thrombolysis, revision) |
| Inflammation / sensitivity to device materials |
| Invasive surgical procedure |
| Kinking |
| Low flow |
| Neointimal hyperplasia |
| Pain |
| Primary graft failure |
| Pseudoaneurysm |
| Seroma |
| Skin erosion; lesion |
| Slow wound healing |
| Steal syndrome |
| Stenosis |
| Swelling of the implanted limb |
| Thrombosis / occlusion, graft |
| Thrombosis, other |
| Ultrafiltration |

All AEs will be collected from the start of treatment until the final follow-up visit at the time points specified in the SoA's (Table 1a and Table 1b).

Medical occurrences that begin before the graft implantation procedure, but after obtaining informed consent will be recorded on the Medical History/Current Medical Conditions section of the CRF, not the AE section.

Artegraft, Inc.
Protocol: ARTCT.BEACH.001

Version 4.0 CONFIDENTIAL

21June2019

Page 48 of 81

All SAEs will be recorded and reported to the Sponsor or designee within 24 hours, as indicated in Appendix 4. The Investigator will submit any updated SAE data to the Sponsor within 24 hours of it being available.

Investigators are not obligated to actively seek AE or SAE after conclusion of the study participation. However, if the Investigator learns of any SAE, including a death, at any time after a patient has been discharged from the study, and he/she considers the event to be reasonably related to the study device or study participation, the Investigator must promptly notify the Sponsor.

The method of recording, evaluating, and assessing causality of AE and SAE and the procedures for completing and transmitting SAE reports are provided in Appendix 4.

10.2.1 Method of Detecting AEs and SAEs (Recording of Adverse Device Effects)

Care will be taken not to introduce bias when detecting AEs and SAEs. Open-ended and non-leading verbal questioning of the patient is the preferred method to inquire about AE occurrences. The graft sites will be assessed for all adverse events during each dialysis treatment.

10.2.2 Investigator Reporting: Notifying the IRB

It is the responsibility of each investigator to submit the protocol, IFU, subject informed consent, subject recruitment materials (if applicable), and other documentation as required by the IRB to their IRB for review and approval. A copy of the written approval must be provided to the contract research organization (CRO). The documentation should clearly mention the approval/favorable opinion of the protocol, the subject informed consent form, and subject recruitment materials (if applicable), including respective version dates. The written approval and a list of members, their titles or occupations, and their institutional affiliations must be obtained from the IRBs and provided to the CRO prior to the release of clinical study supplies to the investigational site and commencement of the study. If any member of the IRB has direct participation in this trial, written notification regarding his or her abstinence from voting must also be obtained.

Each investigator must adhere to all requirements stipulated by their respective IRB. This includes notification to the IRB regarding protocol amendments, updates to the subject informed consent, recruitment materials intended for viewing by subjects, , SAEs and unexpected AEs, reports and updates regarding the ongoing review of the trial at intervals specified by the respective IRB, and submission of final study reports and summaries to the IRB.

10.2.3 Follow-up of AEs and SAEs

After the initial AE/SAE report, the Investigator is required to proactively follow each patient at subsequent visits/contacts. All SAEs, (and non-serious AEs of special interest (as defined in Section 10.2.5)), will be followed until resolution, stabilization, the event is otherwise explained, or the patient is lost to follow-up (as defined in Section 9.4). Further information on follow-up procedures is given in Appendix 4.

10.2.4 Regulatory Reporting Requirements for SAEs

Prompt notification by the Investigator to the Sponsor of an SAE is essential so that legal obligations
and ethical responsibilities towards the safety of patients and the safety of a study device under
clinical investigation are met.

Artegraft, Inc. Version 4.0 21June2019
Protocol: ARTCT.BEACH.001 CONFIDENTIAL Page 49 of 81

- The Sponsor has a legal responsibility to notify both the local regulatory authority and other
 regulatory agencies about the safety of a study device under clinical investigation. The Sponsor will
 comply with country-specific regulatory requirements relating to safety reporting to the regulatory
 authority, Institutional Review Boards (IRB)/Independent Ethics Committees (IEC), and
 Investigators.
- An Investigator who receives an Investigator safety report describing an SAE or other specific safety information (e.g., summary or listing of SAEs) from the Sponsor will review and then file it in the study documentation and will notify the IRB, if appropriate according to local requirements.

10.2.5 Adverse Events of Special Interest

The adverse events of special interest are those of the composite safety endpoint, which include major adverse clinical events (MACE) (e.g., perigraft infection, hemorrhage, , steal, thrombosis, and pseudoaneurysm) within 30 days after first cannulation [Day 0] in the early-access group and in the late-access group.

10.2.6 Stopping Rules

The FDA cleared this device and it has been on the market for more than 40 years. Justifications of the following stopping rules are based on previously published safety data for Artegraft.

Stopping Rules include:

- MACE in more than 20% of early-access patients within 30 days of Day 0
- MACE not listed in Table 4 in early-access patients
- Any SAE not listed in Tables 8 and 9 in early-access patients

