| Patient Number | A total of 50 patients will be randomized to early access, successfully provided early cannulation within 72 hours, and will be followed to 6 months, to provide the data required for submission to the FDA. A 12month assessment for unexpected complications will also be obtained for early access subjects. Patients randomized to the early access group who are not cannulated in the <72-hour period will be followed as a late-access subject |

Artegraft, Inc.
Protocol: ARTCT.BEACH.001

Version 4.0 CONFIDENTIAL 21June2019 Page 9 of 81

| | for 30 days after first cannulation. It is estimated that up to 10 additional patients may fall into this category. A total of 25 patients will be randomized to late access, cannulated at 10 days or later after implant and followed for at least 30 days after first cannulation [Day 0] to assess perioperative major adverse clinical events (MACE) rates and patency data. The late access group will also be assessed for patency at 6 months through a telephone interview or office visit to provide a more robust data set |
|---|---|
| Intervention Description | Patients will be implanted with the Artegraft, for vascular cannulation for hemodialysis, using standard vascular techniques, according to the Instructions for Use. |
| Number of Investigators and Study Centers | Up to five (5) investigational sites are expected to participate in the trial. |
| Study Duration | The enrollment goal is ≥3 patients per site, per month. The anticipated enrollment period is 6 months; the patient enrollment duration for early-access patients is a minimum of 6 months, and total study duration is expected to be 12 months. |
| | The follow-up period on the early access patients will be 6 months and 30 days on the late access patients. In addition, a follow-up telephone call, based on a questionnaire, will be made to the early access patients and/or dialysis centers to determine if any unexpected complications had occurred during the 6-12-month period. For this reason, all patients will be consented to 12 months. The late access group will also be assessed for patency at 6 months through a telephone interview or office visit to provide a more robust data set. |
| Primary Effectiveness Endpoint | Early access success, defined by three cannulations, the first one started within 72 hours after implantation, all with minimum dialysis flow rates of 250 ml/min pump flow rate, with a minimum 17-gauge needle. |

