- 13. History or evidence of severe peripheral arterial disease in the extremity selected for implant (i.e. arterial inflow insufficient to support hemodialysis)
- 14. History of cancer with active disease or treatment within the previous year, except for non-invasive basal or squamous cell carcinoma of the skin
- 15. Bleeding diathesis, other than that associated with ESRD
- 16. Scheduled renal transplant within 6 months
- 17. Patients who require chronic anticoagulation except for antiplatelet therapy. Patients currently receiving or who have received within the last month direct thrombin inhibitors, factor Xa inhibitors, or vitamin K antagonists should not be included in the study.

Artegraft, Inc.
Protocol: ARTCT.BEACH.001

Data Populations

All patients who receive an Artegraft implant will be included in the safety and performance analyses for the device.

The early-access group is composed of the 50 patients that are enrolled, implanted with the Artegraft, successfully provided the first cannulation within 72 hours, and are followed to 6 months. This early-access population will be used to assess Primary, Assisted Primary, and Secondary Patency at 4, 12, and 26 weeks. This early-access population also will be used to assess perioperative major adverse clinical events (MACE) rates, and all adverse events to 26 weeks.

The late-access group is composed of 25 patients that are enrolled, implanted with the Artegraft, that are first accessed at >/= 10 days, and that are followed to 30 days post Day 0. This group will be used to assess perioperative major adverse clinical events (MACE) rates and primary, assisted primary, and secondary patency, at 30 days post Day 0. The late access group will also be assessed for patency at 6 months through a telephone interview or office visit to provide a more robust data set.

Table 1a: Schedule of Assessments (SoA) Early Access Patients

| Procedure | Screening Day -45 to Day of Surgery | Day 0 [1st successful cannulation] (May occur on day of surgery) | Day 1 – 17 Days post Day 0 | Day 30 +/- 3 days post Day 0 | 12 weeks +/- 7 days post day 0 | 6 Months +/- 7 days post day 0 | 12 Months +/- 14 days post day 0* Extended Follow-up |
|--|--|---|--|--|---|---|--|
| Eligibility (inclusion/exclusion) | Х | | | | | | |
| Informed Consent | Х | | | | | | |
| Medical History | Х | | | | | | |
| Prior and concomitant medication | Х | | Х | Х | Х | Х | |
| Physical Exam | Х | | Х | Х | Х | Х | |

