| 12-Lead ECG, when medically indicated | X | | | | | | |
| Vessel mapping (if not done within 8 weeks) | Х | | | | | | |
| Pregnancy test: serum (Women of child-bearing potential only; to be assessed within 7 days of implant) | Х | | | | | | |
| Hematology and coagulation lab test | Х | | | | | | |
| Surgical implant of Artegraft | Х | | | | | | |
| Documentation of surgical procedure | X | | | | | | |
| Assessment of wound healing | | Х | Х | Х | Х | Х | |
| Graft Patency Assessment | Х | Х | Х | Х | Х | Х | Х |
| Adverse event assessment | Х | Х | Х | Х | Х | Х | X ⁺ |
| Medical Device malfunctions | Х | Х | Х | Х | Х | Х | |
| Documentation of graft interventions | X | Х | Х | Х | Х | Х | |
| Use of Dialysis Catheter | | Х | Х | Х | Х | Х | |

These patients will be having dialysis every few days – assessments should be the same or similar at each post-implant visit.

^{*} Extended follow-up will be assessed for patency and AEs only via a telephone follow-up or office visit

⁺ AEs between 6 months and 12 months.

Table 2b: Schedule of Assessments (SoA) Late Access and Early Access Drop-outs

| Procedure | Screening Day -45 to Day of Surgery | Day 0 [1st successful cannulation] (May occur on day of surgery) | Day 1 – 17 Days post Day 0 | Day 30 +/- 3 days post Day 0 | 6 Months +/- 7 days post day 0* Extended Duration Follow-up |
|--|--|---|----------------------------------|--|---|
| Eligibility (inclusion/exclusion) | Х | | | | |
| Informed Consent | Х | | | | |
| Medical History | Х | | | | |
| Prior and concomitant medication | Х | | Х | Х | |
| Physical Exam | Х | | X | Х | |
| 12-Lead ECG, when medically indicated | Х | | | | |
| Vessel mapping (if not done within 8 weeks) | Х | | | | |
| Pregnancy test: serum (Women of child-bearing potential only; to be assessed within 7 days of implant) | X | | | | |
| Hematology and coagulation lab test | Х | | | | |
| Surgical implant of Artegraft | Х | | | | |
| Documentation of surgical procedure | Х | | | | |
| Assessment of wound healing | | Х | Х | Х | |
| Graft Patency Assessment | Х | Х | Х | Х | Х |
| Adverse event assessment | Х | Х | Х | Х | X ⁺ |
| Medical Device malfunctions | Х | Х | Х | Х | |
| Documentation of graft interventions | Х | Х | Х | Х | |
| Use of Dialysis Catheter | | Х | Х | Х | |

These patients will be having dialysis every few days – assessments should be the same or similar at each post-implant visit.

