4.0 OBJECTIVES AND ENDPOINTS

Table 6: Study Objectives and Endpoints

| able 0. Study Objectives and Endpoints | | | | |
|---|---|--|--|--|
| Study Objective | The objective of the BEACH Trial is to demonstrate that early access of Artegraft is associated with acceptable rates of successful early access, and acceptable rates of a composite of adverse events, to support a modification of existing device labeling stating that Artegraft is capable of cannulation within 72 hours post implantation. | | | |
| Primary Effectiveness Endpoint | Early access success, defined by three cannulations, the first one started within 72 hours post implantation, all with minimum dialysis flow rates of 250 ml/min pump flow rate, with a minimum 17-guage needle. | | | |
| | Expectations: $^{\sim}80\%$ of patients in the early access group will have first cannulation within 72 hours. | | | |
| | Expectations: ~90% of patients receiving early access will have 3 successful cannulations. | | | |
| Primary Safety Endpoint | A composite of major adverse clinical events (MACE) including perigraft infection, hemorrhage, thrombosis, steal syndrome, and pseudoaneurysm within 30 days after first cannulation [Day 0] in the early-access and late-access groups. | | | |
| | Expectation: ~20% of patients will have at least one MACE event; no significant difference in event number or type between early and late access groups. | | | |
| | All MACE will be adjudicated by an independent accessor. | | | |
| Secondary Effectiveness Endpoints | Patency (Primary, Assisted Primary, and Secondary) at 30 days after first successful cannulation [Day 0], and at 12 weeks and 6 months after implantation in the early-access group and at 30 days post-Day 0 in the lateaccess group. The late access group will also be assessed for patency at 6 months through a telephone interview or office visit to provide a more robust data set. | | | |
| | Expectations: | | | |
| | Patency rates [all 3 types] at 30 days will be similar in the early and late access groups. | | | |
| | We expect primary patency to be ≥85%, ≥75% and ≥65% at 30 days, 3 months, and 6 months, respectively. | | | |
| | Primary-assisted patency rates at 30 days, 3 months, and 6 months will be ≥85%. | | | |
| | Secondary patency rates will be ≥90% and ≥90% at 3 and 6 months, respectively. | | | |

Artegraft, Inc.
Protocol: ARTCT.BEACH.001

Version 4.0 CONFIDENTIAL 21June2019 Page 29 of 81

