10.3 Interim Analyses

No interim analyses for safety or efficacy are planned.

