10.4 Safety Monitoring

The principal investigator at each site will perform the initial characterization of each serious event. Reports of serious events will be sent to an independent assessor with expertise in vascular access devices who will evaluate serious device related events, MACE, or device malfunctions for level of seriousness and relationship to device or procedure. Reports of serious adverse events also will be reported to each IRB.

Artegraft, Inc. Version 4.0 21June2019
Protocol: ARTCT.BEACH.001 CONFIDENTIAL Page 51 of 81

An independent accessor will be established to enhance the safety of subjects participating in the study. The accessor will adjudicate all possibly and definitely device and procedure-related serious adverse events and will act as an advisor to Artegraft through the CRO. Individual will be represented from the one of the key medical disciplines involved with the care of ESRD patients and management of AV access. Accessor will not be directly involved with the clinical trial and all will possess experience with clinical trial participation or management in the ESRD or AV access space. Accessor's primary responsibilities are to monitor the safety of trial participants, to review safety-related data, to evaluate the frequency and severity and device-relatedness of adverse events, and to consider external data throughout the duration of the trial, and to make recommendations on trial changes.

Artegraft, Inc.
Protocol: ARTCT.BEACH.001

Version 4.0 CONFIDENTIAL

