- The Investigator will submit any updated SAE data to the Sponsor, IRB or CRO within 24 hours of receipt of the information.

Action Taken

- None
- Treatment required
- Hospitalization
- Patient withdrawn
- Administration of study therapy temporarily interrupted
- Administration of study therapy permanently discontinued
- Other (specify)

Outcome

- Recovered, with sequelae
- Recovered, without sequelae
- Improved
- Ongoing
- Death
- Lost to follow-up

Reporting of SAEs

SAE Reporting to Sponsor or the CRO via an Electronic Data Collection Tool

- The primary mechanism for reporting an SAE to Sponsor or the CRO will be the electronic data collection tool.
- If the electronic system is unavailable for more than 24 hours, then the study center will use the paper SAE data collection tool (see next section).
- The study center will enter the SAE data into the electronic system as soon as it becomes available.
- After the study is completed at a given study center, the electronic data collection tool will be taken off-line to prevent the entry of new data or changes to existing data.
- If a study center receives a report of a new SAE from a patient or receives updated data on a previously reported SAE after the electronic data collection tool has been taken off-line, then the study center can report this information on a paper SAE form (see next section) or to the medical monitor by telephone.

SAE Reporting via Paper CRF

- Facsimile transmission of the SAE paper CRF is a secondary method to transmit this information to the medical monitor.
- In rare circumstances and in the absence of facsimile equipment, notification by telephone is acceptable with a copy of the SAE data collection tool sent by overnight mail or courier service.
- Initial notification via telephone does not replace the need for the Investigator to complete and sign the SAE CRF pages within the designated reporting time frames.
- The Medical Monitor is the contact for SAE reporting.

All SAEs will be forwarded to the independent assessor within 72 hours of receipt by Artegraft. The assessor has the discretion to convene a teleconference at any time to discuss the safety of the Artegraft and may recommend modification or termination of ongoing studies. The assessor or the clinical monitor will inform the Sponsor and IRB of any SAE.

Artegraft, Inc. Version 4.0 21June2019
Protocol: ARTCT.BEACH.001 CONFIDENTIAL Page 73 of 81

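### The first stopping rule sets its MACE limit at the rate the plan expects, so a trial running to plan meets it about 4 times in 10; the second refers to a table that omits foreseen MACE components

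*Combined protocol and SAP*

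**What the plan says.** Section 10.2.6 gives three stopping rules and says that they rest on published Artegraft safety data, without giving a figure. The first is "MACE in more than 20% of early-access patients within 30 days of Day 0". The second is met by a MACE in early-access patients that is not listed in Table 4. Section 4.0 states, for the same composite and the same 30-day window, "Expectation: ~20% of patients will have at least one MACE event", with no significant difference foreseen between the groups.

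On who counts, the synopsis says "The early-access group is composed of the 50 patients that are enrolled", implanted, first cannulated within 72 hours and followed to 6 months. Patients randomized to early access who miss that window (up to 10, section 6.8) "will be followed as a late-access subject", and their visit schedule is headed "Late Access and Early Access Drop-outs". Section 9.2.2, however, reports MACE by randomized group.

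On when the limit is applied, section 10.3 says "No interim analyses for safety or efficacy are planned". Section 10.4 gives the independent assessor the task "to evaluate the frequency and severity and device-relatedness of adverse events" over the whole trial. Appendix 4 adds that the assessor "may recommend modification or termination of ongoing studies". Section 11.0 mentions real-time automated analyses in the database. None of these places says how or when the 20% limit is checked.

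**The concern.** A stopping limit placed exactly at the expected rate leaves no room for sampling error. A trial that behaves as the sponsor predicts then has a substantial chance of meeting its own stopping rule, with a 50-patient data set intended for an FDA submission at stake. The size of that chance also depends on how often the limit is checked and on which denominator, and the plan fixes neither.

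The second rule has a related conflict. It treats any MACE type missing from one table as grounds for stopping. That table does not contain every event the plan itself defines as MACE and lists as expected. One foreseen event could therefore meet a stopping rule, perhaps without anyone having intended it.

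**Working it through.** The plan states no operating characteristic for these rules, and section 9.1 says the sample size is logistical, so there is no stated figure to reproduce.

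**Rule 1, inputs.** Limit: above 20% (section 10.2.6). Expected rate: about 20% (section 4.0). Denominator: 50 (synopsis, section 9.1), or up to 50 + 10 = 60 if all patients randomized to early access count (section 6.8).

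**One check.** 20% of 50 is 10, so crossing needs at least 11 patients:

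P(X ≥ 11) = Σ C(50, x) · 0.2^x · 0.8^(50−x), x = 11 to 50, = 0.416.

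20% of 60 is 12, so crossing needs at least 13, with probability 0.424. The choice of denominator hardly matters to this figure.

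**Fixed denominator of 50.** If the rule means the 11th MACE patient among the 50, the total is 0.416 on any schedule. At a true 20%, the chance that the 11th has occurred by patient n is P(X ≥ 11 | n, 0.2): 0.6% by patient 25, 2.6% by patient 30 and 16% by patient 40. Most of the crossing is late.

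**Running proportion.** Let f(n, x) be the probability of x MACE patients among n with no crossing so far. Then f(n, x) = (1−p)·f(n−1, x) + p·f(n−1, x−1), and at each check the mass with x > 0.2n is removed and counted as crossed. Outcomes are treated as known at the check. The schedules are my assumptions.

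| True MACE rate | Once at 50 | At 25 and 50 | Every 10 | Each patient from the 10th |
|---|---|---|---|---|
| 10% | 0.9% | 4% | 10% | 21% |
| 15% | 12% | 21% | 32% | 50% |
| 17% | 22% | 32% | 44% | 62% |
| 20% | 42% | 52% | 62% | 77% |
| 25% | 74% | 80% | 85% | 93% |
| 30% | 92% | 94% | 96% | 98% |

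The smallest crossing count, 11/50 = 22%, has an exact 95% confidence interval of 11.5% to 36.0%.

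**Rule 2, sources side by side.**
- The list of tables and section 3.3 identify Table 4 as the risk analysis. In the body the same table is captioned Table 5.
- Its rows are graft infection, hemorrhage or hematoma, needle-hole bleeding, occlusion and inability to cannulate.
- Pseudoaneurysm is a MACE component in the synopsis, section 4.0 and section 10.2.5. It is not in the table.
- Steal is a MACE component in sections 4.0 and 10.2.5 but not in the synopsis. It is not in the table.
- Section 10.2 lists both among the expected device-related events.
- The third stopping rule cites Tables 8 and 9. These are the expected-event tables only under the numbering of the list of tables, which supports reading Table 4 as the risk analysis.
- Under the body captions, Table 4 is the patency table. It lists no adverse events, so every MACE would meet rule 2.

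The documents give no 30-day rate for pseudoaneurysm or steal. At an assumed combined rate q per patient, the chance of at least one event in 50 is 1 − (1−q)^50: 22% for q = 0.5%, 39% for 1% and 64% for 2%.

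**The case against.** The best defence is that a strict limit is a legitimate cautious choice and that oversight is continuous. Serious events go to the assessor within 72 hours of receipt by the sponsor (Appendix 4), all MACE are adjudicated (section 4.0), and the database analyses data in real time (section 11.0). Planning no interim analysis does not conflict with that. No passage makes crossing an automatic termination. All of this stands, so a reader should not infer that patients are unprotected or that 42% is the probability of the trial being terminated. It is the probability that the rule is met.

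A second defence is that the 42% describes a late check. One look at 50 patients with 30-day data comes after all 50 early cannulations, when mainly follow-up is left to stop. On the fixed-denominator reading, early crossing is uncommon. This also stands, and the 52% to 77% figures apply only if a running proportion is checked repeatedly.

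Third, the true rate may be below 20%. Section 3.2 cites one early-access series with no early graft infection, thrombosis or bleeding, and another with 17% overall complications where early meant within seven days. Neither measures this trial's MACE. At a true 15% or 10% the single-check figure falls to 12% or 0.9%. But about 20% is the plan's own stated expectation.

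Finally, the table behind rule 2 covers risks of early access, so its omissions could be deliberate. Nothing in the plan says so.

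**Conclusion.** The point holds. Rule 1 puts the limit at the expected rate, and at a true 20% it is met with probability 42% at one check of 50 (42.4% of 60). More frequent checks of a running proportion raise this, under assumed schedules. The figure rests on independent patients and a true rate of exactly 20%.

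A reader might go further and infer that crossing cannot tell an expected rate from a high one. The table does not support that: at n = 50 the crossing probability climbs from 0.9% at a true 10% to 92% at 30%. The weakness is confined to the region around the expected rate. Nor is any type I error rate affected, since section 9.1 tests no hypothesis.

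On rule 2, the conflict for pseudoaneurysm holds under all three MACE definitions. For steal it depends on which definition governs, because the synopsis omits it. That one event suffices is the natural reading but not an explicit one: rule 3 refers to any SAE, while rule 2 does not use that word.

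**What to change.** In section 10.2.6, reconcile the 20% limit with the expectation of about 20% in section 4.0, or state that their equality is intended. Report there the crossing probabilities over a range of true rates, so that the sponsor and the independent assessor can decide how the limit is to be used. State when the limit is checked. Define a denominator that can be determined at the time of the check and that keeps patients who die or withdraw before 30 days. The synopsis group cannot serve mid-trial as written, because its membership depends on follow-up to 6 months.

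Reconcile rule 2 and its table reference with the three MACE definitions and the expected-event list, or state that a stop on pseudoaneurysm or steal is intended. The table numbers cited in rule 3 need the same check against the body captions.

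I propose no particular limit and no consequence of crossing. The cost is protocol wording and a small tabulation, with no new data. If the sponsor chose to move the limit upward, sensitivity to a truly high rate would fall from the present 74% at a true 25% and 92% at 30% (one check of 50). The tabulation would make that trade-off visible.
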